4.4.2 Data Collection and Follow-up for Withdrawn Subjects

Patients may be withdrawn from the study if an adverse event occurs which could be attributable to the Janssen Ad26.CoV2.S vaccine or related study procedures, or if patients choose to no longer participate in the study. Once patients are withdrawn from the study, or choose to no longer participate, no further study data will be acquired. If withdrawal occurs before study completion, the reason for withdrawal will be documented in the eCRF and in the source document.

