4.4 Early Withdrawal of Subjects

4.4.1 When and How to Withdraw Subjects

Vaccination with the Janssen Ad26.CoV2.S vaccine will be withheld from participants from Segment I for the reasons listed below. These participants must not receive any further doses of the Janssen Ad26.CoV2.S vaccine but can remain in the study for follow-up assessments of safety and immunogenicity. Additional unscheduled visits may be performed for safety/reactogenicity reasons, if needed. In case of questions, the study staff at Mayo Arizona, Florida or Rochester are encouraged to contact the sponsor-investigator.

- Any related AE, worsening of health status or intercurrent illness that, in the opinion of the sponsor-investigator, requires discontinuation from the Janssen Ad26.CoV2.S vaccine
- The participant becomes pregnant
- Withdrawal of consent to receive the Janssen Ad26.CoV2.S vaccine
- Anaphylactic reaction following vaccination with the Janssen Ad26.CoV2.S vaccine, not attributable to causes other than vaccination
- SAE or other potentially life-threatening (Grade 4) event that is determined to be related to the Janssen Ad26.CoV2.S vaccine
- Participant previously experienced TTS or HIT
- Participant previously experienced myocarditis and/or pericarditis.

A participant will be withdrawn from the study for any of the following reasons:

- Lost to follow-up
- Withdrawal of Consent from the study
- Repeated failure to comply with protocol requirements
- Death

If a participant is withdrawn from the study, or chooses to no longer participate, no further study data will be acquired but their clinical care will continue as usual.

If a patient is withdrawn, but has already received the Janssen Ad26.CoV2.S vaccine, they will not be replaced by another patient.

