7.5 Stopping Rules

Discontinuation of Study Vaccination

Study vaccinations will be withheld for the reasons listed below. These participants must not receive any further doses of Janssen Ad26.CoV2.S vaccine but should remain on study for follow-up with assessments of safety and immunogenicity as indicated in the Schedules of

Activities. Additional unscheduled visits may be performed for safety/reactogenicity reasons, if needed. In case of questions, the investigator is encouraged to contact the sponsor.

- Any related AE, worsening of health status or intercurrent illnesses that, in the opinion of the sponsor-investigator, requires discontinuation from Janssen Ad26.CoV2.S vaccine
- The participant becomes pregnant
- Anaphylactic reaction following vaccination, not attributable to causes other than vaccination
- Platelet Count <75,000 prior to receiving the Janssen Ad26.COV2.s vaccine
- SAE or other potentially life-threatening (Grade 4) event that is determined to be related to Janssen Ad26.CoV2.S vaccine
- Participant received any experimental medication (including experimental vaccines other than the Janssen Ad26.CoV2.S vaccine) or received a COVID-19 vaccine or treatment
- Withdrawal of consent to receive further study vaccination
- Participant has a molecularly confirmed SARS-CoV-2 infection based on samples collected within the study (see Section 7.2.1)
- Participant previously experienced TTS, Heparin Induced Thrombocytopenia (HIT), Myocarditis or Pericarditis.

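### Section 4.4.2 lets a patient be withdrawn from the study, with all data collection ended, for a possibly vaccine-related adverse event, which contradicts Section 7.5 and puts later safety and outcome data at risk

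*Combined protocol and SAP*

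**What the plan says.** Section 4.4.2 gives two grounds for leaving the study: an adverse event, or the patient's own choice. On the first it says: "Patients may be withdrawn from the study if an adverse event occurs which could be attributable to the Janssen Ad26.CoV2.S vaccine"; the sentence goes on to include related study procedures. The consequence is stated without exception: "Once patients are withdrawn from the study, or choose to no longer participate, no further study data will be acquired". The reason for leaving is to be documented in the eCRF and the source document.

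Section 4.4.1 keeps two lists. The first gives reasons to withhold further vaccine. It includes a related adverse event judged to require this, anaphylaxis, and a related serious or Grade 4 event. These participants "can remain in the study for follow-up assessments of safety and immunogenicity". The second list is introduced by "A participant will be withdrawn from the study for any of the following reasons" and has four entries: loss to follow-up, withdrawal of consent, repeated non-compliance and death. An adverse event is not among them. For anyone who leaves, "no further study data will be acquired but their clinical care will continue as usual".

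Section 7.5 repeats most of the vaccine-withholding list, but says that these participants "should remain on study for follow-up with assessments of safety and immunogenicity".

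**The concern.** Stopping a vaccine and leaving a trial are different events, and the protocol separates them in 4.4.1 and 7.5. Section 4.4.2 merges them for the patients whose later course matters most to the safety assessment. Its trigger is low: possible attribution is enough, and no severity or seriousness is required.

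The primary safety endpoint in Section 3.6 is vaccine-related serious adverse events. The secondary safety endpoints include hospitalization, patient survival and graft survival to 2 years. If follow-up can end because harm is suspected, the missing data are linked to the outcome being measured. The trial runs at three sites, and each could apply a different rule while pointing to protocol text in support.

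**Working it through.** No arithmetic applies, because the point rests on no sample size, power or event count. The check sets the rules side by side.

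| Place | What follows a possibly vaccine-related event |
|---|---|
| 4.4.2 | Study withdrawal permitted; no further data |
| 4.4.1, vaccine-withholding list | No further doses; staying in follow-up is allowed |
| 4.4.1, study-withdrawal list | Adverse event not listed; data stop for those who leave |
| 7.5 | No further doses; staying in follow-up is expected |
| 1.5.7 | Safety monitoring of all participants for 2 years after the last dose |
| 1.5.10, myocarditis and pericarditis | No further doses; patient stays in with full surveillance |
| Benefit-Risk Assessment of Study Participation (after 1.5.10) | Significant abnormalities still present at early withdrawal are followed until resolved or stable |
| 7.1, Serious Adverse Event | Serious events and events of significant interest, with sequelae, are followed throughout the study in vaccine recipients |
| 7.1 Post-study Adverse Event, 7.2, 7.3 | Events are followed until resolved, stable or otherwise explained |

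1. **Overlap.** A related event that leads the sponsor-investigator to stop vaccine falls under both 4.4.2 and 7.5. One permits removal from the study; the other expects the patient to stay. The conflict is direct.

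2. **Data stop.** The last four rows cannot be carried out together with "Once patients are withdrawn from the study, or choose to no longer participate, no further study data will be acquired". The Benefit-Risk text is the clearest case, since it requires follow-up of abnormalities after early withdrawal itself.

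3. **What is kept.** Section 7.3 requires reporting of all serious events and of all adverse events that lead to study discontinuation. Section 4.4.2 requires the reason for withdrawal. The event that prompts withdrawal is therefore captured.

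4. **What is lost.** Everything after withdrawal: sequelae, hospitalization, graft and patient survival, and COVID-19 infection to 2 years. If withdrawal comes before Day 28, the antibody endpoint is missing too. Section 6.9 builds the primary analysis on patients who completed the requirements for that endpoint, so the patient drops out of it. Section 4.4.1 does not replace a patient who leaves after vaccination.

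5. **Effect on estimates.** Section 6.9 censors patients with incomplete follow-up at last contact in any survival analysis. Kaplan-Meier and Cox methods then assume that those censored have the same later risk as those who remain. Under 4.4.2 they would have been removed because of suspected harm. If such patients go on to more graft loss, death or hospitalization, the 2-year rates are understated.

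6. **Comparison within the protocol.** Section 8.1 asks sites to seek permission for at least vital status from subjects who revoke authorization to use their health information. Section 4.4.2 has no such provision for patients removed for an adverse event, who may never have asked to leave.

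**The case against.** Section 4.4.2 is discretionary, so nothing need be lost. Section 4.4.1 says only that such patients "can remain in the study for follow-up assessments of safety and immunogenicity", which is compatible with a discretionary withdrawal. Its four reasons are those for which withdrawal is mandatory, and it does not call the list exhaustive. It also repeats the data stop, so on data collection it agrees with 4.4.2. The sections that follow events to resolution show that the intent was not to abandon patients with events. All of this stands. It means that 4.4.1 sits poorly with 4.4.2 rather than flatly contradicting it, and that the loss is possible rather than certain. It does not remove the conflict with 7.5 or with the follow-up rules.

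Three stronger readings are tempting, and the documents do not support them.

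- **A count of patients lost.** Section 1.5.3 reports severe solicited systemic events in 5.3% at the 5×10^10 vp dose, and 0.053 × 400 = 21.2 might suggest about 21 patients. That figure is not a withdrawal rate. It comes from pooled studies of other Ad26 vaccines, mostly describes short-lived malaise and fatigue, and is not an upper bound. The same section gives 64.5% with any solicited systemic event, or 0.645 × 400 = 258, and 4.4.2 sets no severity threshold.
- **Loss of the primary safety endpoint.** The event that prompts withdrawal is still reported under 7.3. Only later events are exposed.
- **A biased randomized comparison.** Both arms receive the same vaccine dose, and no reason is given for vaccine-related withdrawals to differ by arm. A difference could arise if related study procedures were read to include the immunosuppression adjustment, which only one arm undergoes in Segment I. The text does not say so.

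**Conclusion.** The inconsistency is real and should be corrected. Section 4.4.2 directly contradicts 7.5 and cannot be followed together with the rules in 1.5.7, 1.5.10, the Benefit-Risk Assessment, 7.1, 7.2 and 7.3. Sections 4.4.1 and 7.5 also differ from each other, one permitting and the other expecting continued follow-up.

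The exposure is limited to data after the event. Its size cannot be estimated, because the documents give no rate of study withdrawal for adverse events. The statistical consequence rests on two assumptions: that some investigators would use the permission in 4.4.2, and that patients with suspected harm differ from others in later risk. If both hold, the planned censoring is informative.

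**What to change.** Reconcile Sections 4.4.1, 4.4.2 and 7.5, together with 1.5.10, the Benefit-Risk Assessment, 7.1, 7.2 and 7.3, so that three things are defined separately: discontinuing vaccination, leaving the study and ending data collection. Which clinical rule applies after an adverse event is for the sponsor-investigator to settle; this review takes no position on it.

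Amend the data-stop sentence in both 4.4.1 and 4.4.2. Changing 4.4.2 alone would leave the same sentence in force in 4.4.1. For everyone who has not withdrawn consent, the text should keep collection of the Day 28 antibody level, serious adverse events, graft status and vital status.

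The means already exist. Day 28 is a scheduled visit, Section 6 allows blood samples to be sent in by kit, and Section 6.1.7 obtains Year 1 and Year 2 status from the medical record. The cost is a short text amendment to two subsections and a little extra follow-up.

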4.5 Criteria for Temporarily Delaying Administration of Study Vaccination

The following events constitute a temporary contraindication to study vaccination:

- Clinically significant acute illness at the time of vaccination. This does not include minor illnesses, such as diarrhea or mild upper respiratory tract infection.
- Fever (body temperature $\geq 38.0^{\circ}\text{C}/100.4^{\circ}\text{F}$) within 24 hours prior to the planned time of vaccination.
- An illness which in the judgement of the sponsor-investigator may interfere with reactogenicity.
- Additional adjustment needed to immunosuppression medication.

If any of these events occur at the scheduled time for receiving the first dose of the Janssen Ad26.CoV2.S vaccine, randomization at a later date within the screening window is permitted at the discretion of the sponsor-investigator.

If randomization cannot occur within the screening window, the COVID spike protein test will be repeated. If any of these events occur at the scheduled time for the second vaccination, the vaccination can be rescheduled, as long as this is in agreement with the allowed windows (see Visit Windows in the Schedules of Activities).

If the second vaccination visit cannot be rescheduled within the allowed window or the contraindications to vaccination persist, the sponsor-investigator should be contacted for further guidance.

For randomized participants who could not be administered with the Janssen Ad26.COV2.S vaccine on the day of randomization for any reason, vaccination can be administered on another day provided that vaccination occurs within the 28-day screening visit window. Baseline visit procedures should be performed prior to vaccination and within the visit window. The following study visits and procedures will be adjusted accordingly.

Participants who cannot be dosed within the 28-day screening window should be discontinued from the study and should not be rescreened.

5 Study Drug

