5.2.2 Janssen Ad26.CoV2.S Vaccine Dosing

There are no required medications pre or post vaccination with the Janssen Ad26.COV2.s vaccine. Dosage of study drug is defined as such:

- A single 0.5 mL dosage administered via an intramuscular injection. Typical administration time is less than a minute.

For Segment I, vaccination with the Janssen Ad26.COV2.s vaccine will occur 2 weeks post randomization in the no change in immunosuppression medication group (see Schedule of Events 2B). For those who will have an adjustment to their immunosuppression medication (see Schedule of Events 2C) vaccination with the Janssen Ad26.COV2.s vaccine will be 2 weeks after medication adjustment.

In Segment II, vaccination with the Janssen Ad26.COV2.s vaccine will occur three weeks after the result from the anti-SARS-CoV-2 spike protein test results which will be obtained on Day 28 of Segment I. On Day 42 the subject will begin immunosuppressive adjustment and the 2nd vaccination will be on Day 56.

There is no treatment for the Initial Responder group.

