6.1 Segment I

6.1.1 Day - 21 (-30 /+7 Days)

Potential subjects will be identified by review of their medical record. If a participant is identified by review of the report, they will be contacted via the Mayo Clinic portal, the online patient communication system, phone or e-mail (if the potential subject has already contacted the study team in this manner). Study details, procedures, risks, and benefits will be described to patients interested in participation. Subjects will be consented for study participation either via telephone or at Mayo Clinic, depending on patient preference. The participant's medical history, demographics, concomitant medications and therapies, immunosuppression medications and clinical outcomes (current health and graft status) will be collected. Subjects will complete the COVID-19 Surveillance and Evaluation questionnaire (Section 14.6). Relevant medical procedures which are performed as part of the participants clinical care up to 60 days prior to signing of consent, such as clinical laboratory results may be used for determining study eligibility.

Blood for anti-SARS-CoV-2 spike protein antibody and anti-SARS-CoV-2 nucleocapsid total antibody testing will be drawn locally and sent overnight to Mayo Clinic-Rochester Laboratory for

testing. Not all screening procedures need to occur in one day. After consent is obtained, screening procedures can be completed on any day up to the baseline visit.

Patients who meet criteria will be contacted and scheduled to receive the Janssen Ad26.CoV2.S vaccine. They will be required to travel to one of the 3 Mayo Clinic transplant centers to receive the vaccine. There will be 3 groups:

1. Low-responders (n=100)
2. Non-responders (n=300)—Randomized after obtaining evidence that anti-SARS-CoV-2 spike protein antibody levels = 0 U/mL. Patients are stratified by the number of mRNA vaccines they received (2 or more).
 - a. Dosing with the Janssen Ad26.COVID-19 vaccine without immunosuppression adjustment
 - b. Dosing with the Janssen Ad26.COVID-19 vaccine with immunosuppression adjustment.

Subjects randomized to receive immunosuppression adjustment will follow one of the regimens outlined in Section 5.2.1. If randomized to the immunosuppression group, they will be contacted via phone by a physician with instruction on the participant's new immunosuppression regimen.

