6.1.2 Day -14 (+/-3 Days) Non-Responder Group Immunosuppression Change ONLY

Study team will contact the subject and document their immunosuppression medication and instruct the participant to begin their new immunosuppression medication regimen. Patient and graft status information will be recorded as well as the COVID-19 surveillance information collected.

For a subset of patients randomized to receive immunosuppression adjustment: prior to the adjustment the study team will send a kit for a local blood collection for Total Immunoglobulin levels and T-/B-cell immunophenotyping. These specimens will be shipped back to Mayo Rochester via overnight courier for testing.

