6.1.3 Baseline Visit (-4/+1 Day)

Subjects will return to Mayo Clinic for an in-person visit. Prior to receiving the Janssen Ad26.COVID-19 vaccine, the following study procedures will be performed:

- Serum pregnancy test for females of childbearing potential.
- Platelet count

- Mechanistic Studies
- Tacrolimus, Cyclosporine and MMF serum drug levels in subjects who are receiving these drugs or who were receiving these drugs at the time of enrollment.
- Anti-SARS-CoV-2 spike protein antibody and anti-SARS-CoV-2 nucleocapsid total antibody test
- The participant will have a nephrology consult and a complete physical exam (including review of concomitant medications and immunosuppression). The nephrologist will confirm with the IS reduction group that they have complied with their new medication regimen.
- Vital Signs (heart rate, blood pressure, temperature, pulse oximetry, height and weight).
- Asked if they are experiencing any COVID-19 symptoms or have been recently tested.

Eligible subjects will be vaccinated after these procedures have been completed. The following study procedures can be completed at any time during the visit:

- Study team will record concomitant medications and therapies.
- Study team will document immunosuppression medication
- Patient Status and Graft Status
- Risk Factor Assessment (see Section 14.5)
- Safety Follow Up Questionnaires (questions related to potential GBS, TTS, myocarditis and pericarditis symptoms)
- Kidney Transplant Follow-Up Questionnaire

To differentiate symptoms potentially related to the Janssen Ad26.COV2.S vaccine, the participant will be asked about any symptoms they may currently be experiencing prior to vaccination as well as after to differentiate potential vaccine related adverse events. Then they will receive the Janssen Ad26.COV2.S vaccine during a clinical appointment. All vaccination will be monitored post vaccine for 30 minutes for potential reactions to the vaccination.

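### The 28-day dosing limit in section 4.5 has no stated start, does not match the screening schedule, and removes undosed randomized patients from follow-up

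*Combined protocol and SAP*

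**What the plan says.** Section 4.5 covers temporary delays to vaccination. A randomized participant who could not be vaccinated "on the day of randomization for any reason" may be vaccinated on another day, "provided that vaccination occurs within the 28-day screening visit window". The section ends: "Participants who cannot be dosed within the 28-day screening window should be discontinued from the study and should not be rescreened". For participants not yet randomized it has a different rule: "If randomization cannot occur within the screening window, the COVID spike protein test will be repeated".

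The timing of Segment I is set elsewhere:

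- Section 6.1.1 and Schedules of Events 2A to 2C put the screening visit at Day -21, up to 30 days earlier or 7 days later. Section 6.1.1 also lets individual screening procedures be done on any day up to baseline.
- Section 6.1.3 puts the dosing visit at Day 0, with a window of -4/+1 day.
- Section 5.2.2 says that vaccination "will occur 2 weeks post randomization in the no change in immunosuppression medication group". In the other arm it follows the medication adjustment by two weeks. Section 6.1.2 places that adjustment at Day -14, plus or minus 3 days.
- Sections 5.2.1 and 6.1.5 time the return to prior immunosuppression at 28 days after the dose.

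On follow-up, section 4.4.1 says that participants whose vaccination is withheld can stay in the study, and section 7.5 says that they should. The section 7.5 reasons include a platelet count below 75,000 before the vaccine. Section 4.4.1 lists the reasons for withdrawal from the study, and a missed dosing window is not among them. Sections 4.4.1 and 4.4.2 say that no further study data are acquired after withdrawal.

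**The concern.** Two things look wrong.

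First, a site cannot tell when the 28 days begin: consent, screening visit, spike antibody sample or randomization. On the most natural reading of a screening window, the limit is tighter than the schedule, so a patient can meet every visit window and still be due for discontinuation.

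Second, the consequence falls after randomization. A non-responder whose dose is delayed past the limit is to leave the study. In the adjusted arm this can happen after maintenance immunosuppression has been changed. Section 1.5.9 acknowledges a possible risk of rejection or graft loss from that change, asks the DSMB to monitor it, and pauses the study at a 10% rejection rate. Section 3.6 counts patient survival, graft survival and hospitalization from randomization, and lists adverse events of immunosuppression reduction. Patients who were exposed but never dosed belong in those data, and section 4.5 as written can take them out. Nor does the protocol say when they go back to their usual regimen.

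**Working it through.** **Can 28 be reproduced from the schedule?** Inputs: screening at Day -21 with -30/+7 days (6.1.1, Schedules 2A to 2C).

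- Nominal gap to dose: 21 days.
- Latest screening: -21 + 7 = Day -14, a gap of 14 days.
- Earliest screening: -21 - 30 = Day -51, a gap of 51 days.
- Width of the window: 30 + 7 = 37 days, so 38 calendar days counted inclusively.

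None of these is 28. A limit of 28 would follow from an early tolerance of 7 days (21 + 7 = 28), but the schedule allows 30.

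**Which permitted screening days break a limit counted from screening?** The condition is dose day minus screening day greater than 28.

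| Dose day | Interval from screening to dose | Screening days past the limit | Count of 38 |
|---|---|---|---|
| Day -4 | 10 to 47 days | Day -51 to -33 | 19 |
| Day 0 | 14 to 51 days | Day -51 to -29 | 23 (61%) |
| Day +1 | 15 to 52 days | Day -51 to -28 | 24 |

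**When does the limit expire relative to the adjustment?** In the adjusted arm, take a limit at screening day + 28, adjustment on day A, and dose on Day 0. The limit falls on or after the adjustment but before the dose for:

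- A = Day -14: screening on Day -42 to -29, 14 days.
- A = Day -17: screening on Day -45 to -29, 17 days.
- A = Day -11: screening on Day -39 to -29, 11 days.

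**What if screening is on the nominal day and the dose is delayed?** Screening on Day -21 puts the limit at -21 + 28 = Day 7, so 7 days of delay are allowed. With adjustment on Day -14, an adjusted-arm patient who reaches that limit undosed has had 14 + 7 = 21 days of changed immunosuppression.

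All of these are calendar days, not patients. No figures are given for a clock that starts at randomization, because the documents do not fix the interval from randomization to dose in the adjusted arm. Section 5.2.2 gives two weeks for the unchanged arm only, and Schedules 2B and 2C mark randomization in the Day -21 column.

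**Sections side by side.** Take a randomized patient found at the baseline visit to have a platelet count below 75,000, which does not recover before the limit. Section 7.5 withholds the vaccine and keeps the patient on study. Section 4.5 discontinues the same patient from the study. Both apply, and they give opposite instructions.

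**The case against.** The strongest reply is that the two windows are compatible. The site chooses the dosing day, so dosing 14 to 28 days after screening satisfies both rules. The nominal Day -21 visit and the 14-day adjustment lead both fit inside that span. This stands: no patient is forced out by the schedule alone. A reader might infer that about 61% of patients would be discontinued. The documents do not support that, since the figure counts permitted days with equal weight and holds Day 0 fixed. A clock started from a later spike sample would also be shorter, although the protocol does not name the sample as the start.

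A second reply is that follow-up is partly protected already. Three of the four delay events in section 4.5 are illness or fever. Sections 4.4.1 and 7.5 both cover intercurrent illness or worsening health that, in the sponsor-investigator's opinion, requires stopping the vaccine. That helps some patients. It does not cover a delay for further immunosuppression adjustment, and it does not remove the opposite instruction in section 4.5.

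A third reply is that 21 days of changed immunosuppression is well within the 14 + 28 = 42 days already planned, and that clinical care continues after withdrawal. That also stands. The gap is the lost data and the missing return instruction, not an exposure beyond plan.

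Finally, a reader might take the reference in section 4.5 to dosing on the day of randomization as contradicting section 5.2.2. It is better read as a clause that permits a later dose. It suggests that the section was not written around the two-week lead, but it is not a contradiction in itself.

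**Conclusion.** The concern holds in a limited form, and the text should be changed. The 28-day limit has no stated start and does not match the screening window. Counted from screening, a patient screened on Day -51 to Day -29 and dosed on Day 0 is on schedule but past it. More important, whichever start is meant, section 4.5 discontinues randomized patients whom section 7.5 would keep whenever vaccination is withheld for one of its listed reasons. It can thereby lose safety and outcome data on adjusted-arm patients whose immunosuppression has already been changed and whose return date is not stated.

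The day counts assume that the limit runs from the screening visit and that Day 0 is fixed. The loss of follow-up assumes that discontinuation in section 4.5 carries the consequence that sections 4.4.1 and 4.4.2 give to withdrawal. The number of patients affected is unknown. A reader might infer lost power or a biased comparison between arms. The documents show neither, and how undosed randomized patients enter the primary analysis is a separate question about section 6.9. Low responders are not randomized, so only the mismatch of windows applies to them.

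**What to change.** 1. In section 4.5, for randomized participants, replace discontinuation from the study with the section 7.5 rule: vaccination is withheld and the participant remains in safety and outcome follow-up.
2. In section 5.2.1, state that adjusted-arm patients who will not be dosed resume their prior immunosuppression promptly.
3. State when the 28 days start and make the two windows agree. The simplest way is to keep 28 days and require that the spike sample used for eligibility be taken no more than 28 days before dosing. If that would be exceeded, repeat the spike test before randomization, as section 4.5 already provides for the screening window.

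Stretching the limit to 52 days to match the present schedule is not advised. For a patient screened on Day -21 it would allow a dose at -21 + 52 = Day 31. In the adjusted arm that means 14 + 31 = 45 days of changed immunosuppression before the dose and 45 + 28 = 73 in all, against the 42 planned.

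The cost is wording in sections 4.5 and 5.2.1, a narrower screening window in section 6.1.1 and Schedules 2A to 2C with some repeat spike tests, and a few follow-up contacts for undosed randomized patients.
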